C.1. Study design. This is a double-blind, 4-intervention, 4-period crossover randomized controlled trial of HFOx, HFAir, LFOx, and LFAir in non-hypoxemic cancer patients (**Figure 3**). We plan to enroll 36 patients in total. The eligibility criteria are listed in **Table 1**. We will use a computer-generated sequence for randomization. Even with 2 different flow rates, patients and research staff will be blinded to the gas (i.e., oxygen v. air) while a separate respiratory therapist will provide the study intervention; thus, this will remain a double-blind study. On the basis of our experience conducting symptom control trials, we believe this study design will not be an undue burden for hospitalized patients (approximately 1-2 hours, including washout).¹⁹ The rationale for the current study design is as follows:

[figure not shown]

Figure 3. Study Flow Chart. In this double-blind, 4-intervention, 4-period crossover randomized controlled trial, all patients will try 10 minutes of each intervention, followed by a variable washout period (purple arrow). The sequences above represent one of the 6 Latin Squares that may be used.

- **Crossover design**—This design allows intra-individual comparison, thus maximizing study power (144 tests in 36 patients) in addition to providing overall preference.²⁰ We use the Latin square design to minimize the sequences needed.
- **Intervention duration**—We will limit this intervention to only 10 minutes in this proof-of-concept study to minimize study burden and attrition, and to examine the effect of short intervention. We expect the effect of gas exchange to be rapid. Previous dyspnea studies with oxygen delivery have utilized similar durations⁸.
- **Variable washout period**—although the washout period is expected to be short (<10 min), it has not been defined. Thus, we will measure dyspnea on the Numeric Rating Scale starting after 10 minutes of each intervention every 5 minutes until patient returns to within 1 point of the baseline level of dyspnea (i.e. immediately prior to starting the first intervention) before we proceed to the next intervention.
- **Inclusion of HFOx, HFAir and LFAir arms**—HFOx has not been tested in non-hypoxemic cancer patients. No published study has examined the therapeutic role of HFAir in any patient population. The efficacy of LFAir has not been studied in the hospitalized population²¹.

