⁴ Heart rate, respiratory rate, oxygen saturation, and transcutaneous CO₂ level will be measured.

⁵ Dry eyes, dry nose, nasal moisture and anxiety will be assessed using a numeric rating scale from 0 (not at all) to 10 (worst possible).

⁶ Dyspnea intensity will be assessed using the NRS scale every 5 minutes until patients return to baseline. The duration of washout is a useful secondary outcome.

⁷ FiO₂, flow rate, and temperature.

⁸ We will assess blinding (oxygen v. air) of patients and research staff after each treatment. At the end of the study, patients will be asked which of the 4 interventions they prefer

D. STATISTICAL CONSIDERATIONS

D.1. Analysis plan.

Design: We propose a 4-period, 4-intervention balanced Latin-square cross-over (Williams) design with 4 sequences and 36 patients (i.e., 9 replicates per sequence). The primary outcome is the Dyspnea Numeric Rating Scale (0-10). Each intervention is 10-minutes long with NRS assessments at 0, 5 and 10 minutes. Washout periods between interventions will continue until NRS assessment returns to within one unit of baseline.

Primary analysis: We will fit a mixed effects linear model to the Dyspnea Numeric Rating Scale data to account for the repeated measurements (i.e. 0, 5 and 10 minutes) which yield period, sequence, and carryover effects and to model the various inter-patient and intra-patient sources of variation. Appropriate data visualization and residual analyses will also be performed. The primary objective of the study is to obtain preliminary estimates of the effect sizes (In a mixed model, the slope of change will provide an estimate of effect size. We will also determine the mean change in NRS over 10 minutes for each study intervention).

Secondary analysis #1: We will estimate the completion rate as the proportion of patients starting treatment that complete all four interventions.

Additional secondary analyses: Using mixed effects linear models we will obtain preliminary estimates of the study effects for physiologic function (oxygen saturation, respiratory rate, transcutaneous CO₂). We will also assess washout period duration in a similar fashion. Finally, we will tabulate patient intervention preferences obtained at the end of the study.

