D.2. Sample size justification. We will enroll 36 patients over 2 years. Although due to the complexity of the statistical models we cannot accurately estimate the precision of our effect estimates, based on our experience with mixed effects models, 36 patients with 12 repeated measurements (3 times for each of 4 interventions) will provide adequate precision. If the completion rate is 80% then with 36 patients, a 95% confidence interval on this estimate would extend from 64% to 92%.

E. DATA CONFIDENTIALITY PROCEDURES

Study data will be collected and managed using REDCap (Research Electronic Data Capture) tools hosted at MD Anderson or hardcopy surveys. Participants will have the option to complete surveys electronically or hardcopy. Data entry of any hardcopy survey will be completed using REDCap software. REDCap (www.project-redcap.org) is a secure, web-based application with controlled access designed to support data capture for research studies, providing: 1) an intuitive interface for validated data entry; 2) audit trails for tracking data manipulation and export procedures; 3) automated export procedures for seamless downloads to common statistical packages; and 4) procedures for importing data from external sources. In the case of multi-center studies REDCap uses Data Access Groups (DAGs) to ensure that personnel at each institution are blinded to the data from other institutions. REDCap (<https://redcap.mdanderson.org>) is hosted on a secure server by MD Anderson Cancer Center's Department of Research Information Systems & Technology Services.

REDCap has undergone a Governance Risk & Compliance Assessment (05/14/14) by MD Anderson's Information Security Office and found to be compliant with HIPAA, Texas Administrative Codes 202-203, University of Texas Policy 165, federal regulations outlined in 21CFR Part 11, and UTMDACC Institutional Policy #ADM0335. Those having access to the data file include the study PI and research team personnel. Users are authenticated against MDACC's Active Directory system. All protected health information (PHI) will be removed from the data when it is exported from REDCap for analysis. Following publication study data will be archived in REDCap.

Health information will be protected and we will maintain the confidentiality of the data obtained from the patient's chart.

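### D.1 takes a straight-line slope over 0, 5 and 10 minutes as its model-based effect size although C.1 expects a rapid effect; time should be a three-level factor

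*Combined protocol and SAP*

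**What the plan says.** Section D.1 (Design) sets the measurement times: "Each intervention is 10-minutes long with NRS assessments at 0, 5 and 10 minutes". The primary analysis is a linear mixed model on all three readings, with period, sequence and carryover effects. The primary objective is the effect size itself, and D.1 names two summaries for it. The first is model-based: "In a mixed model, the slope of change will provide an estimate of effect size". The second follows directly: "We will also determine the mean change in NRS over 10 minutes for each study intervention". D.1 adds a check on the fit: "Appropriate data visualization and residual analyses will also be performed".

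D.1 does not say how time is coded, whether the interventions have separate or shared intercepts, which random effects are used, or which of the two summaries is primary.

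Section C.1, in justifying the 10-minute intervention, says: "We expect the effect of gas exchange to be rapid". Neither C.1 nor any other section says what share of the change in NRS is expected by 5 minutes.

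**The concern.** A slope summarises the response well if dyspnea falls by the same amount from 0 to 5 minutes as from 5 to 10. If relief comes early and then levels off, a line is the wrong shape. Because D.1 does not fix the intercept structure, the same data could then give different effect sizes, or the same effect size with different standard errors, depending on how the analyst reads one sentence.

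This matters because estimation is the primary objective. The effect size and its standard error are what the trial hands on to later work, and the slope is the only summary that D.1 ties to the model.

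**Working it through.** **Inputs.** From the documents: times 0, 5 and 10 minutes; 4 interventions; 36 patients. Assumed, because the documents give no values: patient SD 1.8, patient-by-period SD 0.6, residual SD 0.8, and step effects as stated below. Let d be the true 10-minute effect and f the share of it present at 5 minutes. Data are taken as complete. The plan gives no SD, precision or target effect for the NRS, so it has no figure to reproduce on this point.

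**1. Separate intercept for each intervention.** The slope weights are (t − 5)/Σ(t − 5)² = (t − 5)/50, that is −0.1, 0 and +0.1. Times 10, they are −1, 0 and +1. So slope × 10 is exactly the change from 0 to 10 minutes, for any f. In a simulation with a true difference of −2.0, slope × 10 and the simple mean change both averaged −1.99.

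**2. Standard error in that form when the effect is complete by 5 minutes (f = 1).**
- A line through (0, d, d) has fitted values d/6, 4d/6 and 7d/6, and residuals −d/6, +2d/6 and −d/6. Their sum of squares is d²/6.
- The within-period residual degrees of freedom are 36 × 4 × 2 − 4 = 284.
- Take a 2-point step under both high-flow interventions and none under low flow. Lack of fit adds 36 × (4 + 4)/6 / 284 = 48/284 = 0.169 to the true residual variance of 0.8² = 0.64, giving 0.809.
- The variance of a difference between two values of slope × 10 is 2 × 2σ²/36 = 4σ²/36. Reported SE: √(4 × 0.809/36) = 0.300. Correct SE: √(4 × 0.64/36) = 0.267. Ratio 1.12.
- A fitted model under the same SDs with a full plateau by 5 minutes gave 0.301 against 0.266, a ratio of 1.13.
- With steps of 0, 0.5, 1 and 2 points the added variance is 36 × 5.25/6 / 284 = 0.111, the SE is √(4 × 0.751/36) = 0.289, and the excess is 8%. The inflation therefore depends on the effects as well as the SDs.

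**3. Shared intercept, no patient-by-period variance in the model.** The weights for the between-intervention slope contrast are t/Σt² = t/125. Times 10, they are 0, 0.4 and 0.8. Applied to (0, fd, d), slope × 10 = (0.8 + 0.4f)d.

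| f | slope × 10 ÷ true 10-minute effect |
|---|---|
| 0.5 | 1.00 |
| 0.75 | 1.10 |
| 1 | 1.20 |

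A simulation with f = 1 and only a patient random intercept gave −2.38 for a true −2.0, a ratio of 1.19.

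**4. Shared intercept plus a patient-by-period random intercept, f = 1.** The weights are t′V⁻¹/(t′V⁻¹t) with V = I + kJ, where J is the matrix of ones and k = ICC/(1 − ICC). At ICC 0.5, k = 1 and V⁻¹ = I − J/4, so t′V⁻¹ = (−3.75, 1.25, 6.25) and t′V⁻¹t = 6.25 + 62.5 = 68.75. The ratio is 10 × (1.25 + 6.25)/68.75 = 1.09. The same formula gives 1.14 at ICC 0.25, 1.03 at 0.8 and 1.02 at 0.9.

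**5. Starting levels.** Steps 3 and 4 take equal average levels at time 0. The washout rule allows some departure: "Washout periods between interventions will continue until NRS assessment returns to within one unit of baseline". With a shared intercept as in step 3, a chance gap of +0.5 or −0.5 between two interventions turns a true 1-point step into 1.2 × 1.5 = 1.8 or 1.2 × 0.5 = 0.6. Separate intercepts, or an analysis of change from time 0, avoid this.

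**The case against.** The strongest case against is that D.1 largely protects itself. The mean change over 10 minutes needs no linearity, and the planned plots and residual checks would show a step at 5 minutes. In addition, C.1 speaks of gas exchange, not of dyspnea scores, and is compatible with relief that builds over the whole 10 minutes. D.1's stated aim of modelling the various within-patient sources of variation points towards a patient-by-period effect, which shrinks any bias.

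Most of this stands, and it limits the size of the problem without closing the gap. The mean change is defined for each intervention separately; no between-intervention contrast is stated for it, and it is not named as primary. No action is tied to the residual checks. The random effects are not listed.

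Some stronger readings are tempting and should be resisted.
- A reader might infer that the slope wastes the 5-minute readings (36 × 4 = 144 of 432) because they have zero weight when intercepts are separate. That is not a bias, and with complete data the 0-to-10-minute change in a model with categorical time gives them no weight either.
- A reader might infer that the slope overstates the effect by 20%. That needs a shared intercept, the whole effect by 5 minutes and no patient-by-period variance; the documents state none of these.
- A reader might extend a per-minute slope beyond 10 minutes. The plan makes no such projection.
- A reader might turn this against D.2's statement that "36 patients with 12 repeated measurements (3 times for each of 4 interventions) will provide adequate precision". D.2 concedes that precision cannot be accurately estimated, so the count of 12 is a description and does not need rewording on this account.

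**Conclusion.** The concern holds as a specification weakness of moderate size in a pilot estimation study. A straight-line slope sits poorly with the plan's own expectation of a rapid effect, and D.1 leaves open the choice that decides what follows.

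Separate intercepts leave the estimate unbiased but inflate its standard error if there is an early plateau. The 13% figure rests on the assumed SDs and a full plateau by 5 minutes, and falls to 8% with the smaller set of steps shown. A shared intercept biases the estimate upwards by 0 to 20% for f between 0.5 and 1, given equal average starting levels, and by less once a patient-by-period effect is included. If relief is linear over the 10 minutes (f = 0.5), neither problem arises. Since the documents do not give f, no single figure can be put on the error; the case for change is that a better method is available at almost no cost.

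**What to change.** In D.1, Primary analysis:

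- Model time as a three-level factor (0, 5, 10 minutes) crossed with intervention, with patient and patient-by-period random effects.
- Name the between-intervention contrast in change from 0 to 10 minutes, estimated from this model, as the primary effect size, and the 5-minute contrast as supportive.
- Drop the per-minute slope as an effect size, or label it descriptive.

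This makes no assumption about the time course, so an early plateau no longer enters the residual, and it does not depend on a shared starting level. The cost is one more parameter per intervention (three time-point means in place of an intercept and a slope) and a few lines of wording. No assessment or data collection changes.

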randomized controlled trial comparing HFOx and bilevel positive airway pressure (two hours each) in advanced cancer patients with refractory dyspnea. Twenty-four of 30 (80%) patients completed the study interventions, suggesting that a study of these two devices is feasible in this patient population. HFOx (mean change, 1.9; 95% CI, 0.4-3.4; $P=0.02$) was associated with significant improvements in dyspnea (Figure 2). Remarkably, two patients who completed HFOx reported low dyspnea scores (≤ 2 of 10) up to 1 hour after discontinuing use of the devices. This observation is of particular interest because the mechanical effect of HFOx on breathing effort may have a long-lasting effect on dyspnea. Overall, 10 of 13 (77%) patients who completed HFOx reported dyspnea improvement, with none experiencing significant adverse effects. Of note, this study was conducted in patients who were predominantly hypoxemic (93%) and did not respond to LFOx. These data support the feasibility of conducting a clinical trial with HFOx in cancer patients and provide preliminary evidence of its efficacy. Importantly, HFOx and HFAir have not been formally tested in non-hypoxemic patients, which is why the proposed trial is particularly novel.

[figure not shown]

Figure 2. Improvement in Dyspnea Before and after high flow oxygen (N=15)

B.4. Low-flow supplemental oxygen for non-hypoxemic cancer patients¹⁸. In a double-blind, randomized trial, we found that LFOx at 5 L/min did not improve dyspnea during a 6-minute walk compared with LFAir at 5 L/min. The results of this important

study highlight the lack of efficacy of LFOx for dyspnea in non-hypoxemic patients and the need to evaluate novel treatment options (i.e., HFOx and HFAir).

B.5. Study rationale. We expect to advance our understanding of how HFOx can be used to treat dyspnea in non-hypoxemic cancer patients. The effective management of dyspnea may ultimately help alleviate this devastating symptom. By elegantly dissecting the high-flow mechanism from the oxygen content and capturing changes in physiologic parameters, we will gain a better understanding of the mechanisms that help alleviate dyspnea and devise newer, more effective treatments.

C. RESEARCH DESIGN AND METHODS

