C.6. Blinding. The patients and research staff will be blinded to the assignment of the gas (i.e., oxygen vs. air). The gas will be delivered via gas outlets inside the patient's room, located behind the bed. Only the respiratory therapist administering the gas will be aware of its identity. To ensure proper blinding, the research staff will step out of the room while the respiratory therapist sets up the gas delivery device. The gas supply will be covered with a piece of cloth to ensure proper concealment. The respiratory care specialist will be specifically asked to not to discuss the identity of the study gas. We will assess blinding by asking the patients and study staff about the identity of the gas at the end of study. The flow rate cannot be blinded in this study.

C.7. Study outcomes. See Table 2 for a detailed description of the study assessments. We will also collect data on patient demographics and study feasibility outcomes (rates of enrollment and attrition). The study interventions will be provided to patients while at rest, and dyspnea ratings will only be assessed when patients are at rest.

C.8. Co-interventions. We expect that co-interventions will be minimal because of the short study period. We will document any regularly scheduled, bronchodilators or opioids given 1 hour before or during the study period. However, if patients required as need opioids (for pain or any other reasons) or bronchodilators during the study period, they will need to come off study and will need to be replaced.

C.9. Training of research staff. An orientation will be held with all research staff involved in this study to introduce them to the study design and standardize the provision of each intervention. Particular attention will be paid to ensuring that research staff provide patients with proper instructions so they understand the study assessments. We will also have several mock-ups for practicing the study procedures.

C.10. Data Safety Monitoring Board (DSMB). The MD Anderson DSMB will be providing monitoring for patient safety and data quality assurance purposes.

C.11. Dropouts. Patients will come off study if (1) they decide for any reason to stop; (2) they did not achieve within 1 point of the baseline level of dyspnea after 1 hour during the washout period, (3) they require as need opioids (for pain or any other reasons) or bronchodilators during the study period. These individuals will need to be replaced.

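### Does the planned mixed model of washout duration need a written rule for washouts that end without a return to baseline?

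*Combined protocol and SAP*

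**What the plan says.** Footnote 6 to Table 2 has dyspnea rated "every 5 minutes until patients return to baseline. The duration of washout is a useful secondary outcome". D.1, under the additional secondary analyses, gives linear mixed models for oxygen saturation, respiratory rate and transcutaneous CO₂, and adds: "We will also assess washout period duration in a similar fashion".

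D.1 (Design) sets the end point of each washout: "Washout periods between interventions will continue until NRS assessment returns to within one unit of baseline". C.11 sets the limit. A patient comes off study on choosing to stop, or if "they did not achieve within 1 point of the baseline level of dyspnea after 1 hour during the washout period", or if "they require as need opioids (for pain or any other reasons) or bronchodilators during the study period. These individuals will need to be replaced".

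Three other statements bear on the point. C.1 says that "although the washout period is expected to be short (<10 min), it has not been defined". C.12 expects little attrition. For the completion rate, D.1 uses the "proportion of patients starting treatment that complete all four interventions", so patients who leave early still count there.

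**The concern.** A washout stopped at 1 hour, or earlier because the patient left, has no observed end time. It is right-censored. A linear mixed model needs one number per washout, so the analyst must omit these washouts, enter 60, or enter the exit time. The plan does not choose, and replacing the patient could make omission an easy default.

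Omission removes the longest washouts. Entering early exits as complete shortens them. Either would understate washout length, most of all for the intervention with the longest washouts, and would shrink differences between interventions. Since C.1 says the washout length is unknown, later trials could use this estimate to set their own. B.3 also seems to point to long washouts: two patients in the previous high-flow trial had low scores "up to 1 hour after discontinuing use of the devices".

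**Working it through.** The plan gives no figure for washout duration, so there is none to reproduce. The illustrations below rest on stated assumptions.

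**Number of washouts.** There are 36 patients in 4 sequences of 9 (D.1). If only washouts between interventions count (D.1), each intervention comes last in one sequence, leaving 36 − 9 = 27 washouts per intervention. If the last intervention is also followed by a timed washout, as C.1 and the Figure 3 caption allow, there are 36.

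**At the length the plan expects.** Assume exponential washouts of mean 10, the upper end of C.1's expectation, read at the next 5-minute check with a limit of 60.

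- Share beyond 60: exp(−60/10) = 0.0025, so 27 × 0.0025 = 0.07 washouts per intervention and 108 × 0.0025 = 0.27 in the whole trial (4 × 27 = 108).
- Mean with non-returns as 60: 5(1 − e^−6)/(1 − e^−0.5) = 12.68.
- Mean with non-returns left out: (12.68 − 60 × 0.0025)/(1 − 0.0025) = 12.56.
- Loss: 0.12 minutes, on a scale read every 5 minutes.

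**With no distribution assumed.** Let n returned washouts average μ, and let k more end at 60 without return. Leaving these out lowers the mean by k(60 − μ)/(n + k). With μ = 10:

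| k | n = 27 | n = 36 |
|---|---|---|
| 0 | 0 | 0 |
| 1 | 50/28 = 1.79 | 50/37 = 1.35 |
| 2 | 100/29 = 3.45 | 100/38 = 2.63 |

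One early exit at 10 minutes, added to 27 others averaging 10, gives (270 + 10)/28 = 10.0 if entered as complete and (270 + 60)/28 = 11.8 if taken as not returned by 60. The documents give no basis for any particular k.

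**Where the effect becomes visible.** Compare a high-flow mean of 20 or 30 minutes with a mean of 10, by the same exponential calculation and 27 washouts per intervention.

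| Assumed mean | Difference, non-returns as 60 | Difference, left out | Loss | Approximate SE |
|---|---|---|---|---|
| 20 | 21.48 − 12.68 = 8.80 | 19.46 − 12.56 = 6.90 | 1.90 | 3.66 |
| 30 | 28.16 − 12.68 = 15.48 | 23.18 − 12.56 = 10.62 | 4.87 | 4.15 |

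These are 0.5 and 1.2 standard errors, treating washouts as independent (the last digit of the second row reflects rounding). The second row conflicts with the plan's other expectations. At mean 30, exp(−2) = 0.135 of high-flow washouts reach the limit. Half the sequences have one high-flow washout before the last intervention and half have two, so the share of patients leaving is about (0.135 + 0.252)/2 = 0.194. With the small low-flow contribution this is 7.1 of 36, or 20%. That alone uses up the non-completion A.2 allows (0.20 × 36 = 7.2).

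**If non-returns are entered as 60.** The linear mixed model then estimates mean time to return restricted to 60 minutes, and full-hour non-returns cause no loss against that target.

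**What B.3 shows.** It reports scores of 2 or less after two hours of use in mainly hypoxemic patients. It gives no baseline for the two patients, so it cannot show that they stayed more than 1 point from baseline, which is this trial's criterion.

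**The case for a change.** The strongest case for a change is that C.11 itself foresees washouts of a full hour without return, so the plan should say how they are analysed. Estimation is this outcome's only purpose, and omission, 60 and exit time estimate different things. A sentence in D.1 would settle it with no new data, because dyspnea is already rated every 5 minutes during washout.

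It stands that no rule is written and that a written one would be tidier. It also stands that entering 60 does not settle early exits, which may be related to dyspnea; each leaves the range shown above.

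The harm, however, depends on a choice the plan never states. Coming off study and being replaced is not the same as having recorded data removed, and a mixed model can use the periods a patient did complete. Nor is every non-return a persisting benefit. The criterion is two-sided, so a patient whose dyspnea worsened or fluctuated also fails it, and such a washout says little about the carryover time a later design needs. A frailty or discrete-time model would be heavy for one clause of a pilot analysis.

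**Conclusion.** No change to the plan is needed. This is a gap that an analyst can fill sensibly within the planned model: keep every washout started, enter full-hour non-returns as 60, and report the unfinished ones with their reasons.

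Under the assumed exponential shape at mean 10, even the worst handling of full-hour non-returns costs about 0.1 minute. One omitted non-return would cost 1.4 to 1.8 minutes on a 10-minute average, depending on whether 36 or 27 washouts per intervention are timed. Losses of 2 to 5 minutes in a difference between interventions need high-flow means two to three times the 10-minute figure in C.1. If washouts proved that long, the number of patients leaving under C.11 would make it plain before anyone relied on the mean.

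Washout duration is outside A.1 to A.3 and carries no test or decision. Separately, footnote 6 describes the end of washout differently from C.1, C.11 and D.1. That is a wording matter to be reconciled, and it does not affect this conclusion.
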